# THE MERRILL PALMER SKILLMAN INSTITUTE FOR CHILD & FAMILY DEVELOPMENT

To Whom it May Concern:

Regard: Clinicaltrials.gov documents

Project Title: The Parenting Young Children Check-up: Proof-of-Concept Trial

ID: K01MH110600

Document Date: January 20, 2020

Enclosed are documents to accompany the results of this small proof-of-concept trail. The present investigation is "Phase 2" of the enclosed protocol. Data were collected through Henry Ford Health Systems in the United States between October 22, 2019 and March 4th, 2020. Within this investigation 30 parents were screened and 6 participated in the non-randomized trial. Trial participants went through parent of the Parenting Young Children Check-up intervention while waiting at a pediatric visit. Through mixed methods, parents reported on program ease of use, perceived usefulness, and how much they liked the intervention. Moreover, parents reported if going through the first parent of the program led them to want to use the program parent training website (with video-based content aimed at teaching behavioral parenting skills). This was not a hypothesis driven investigation, but rather an exploration of this mode of intervention delivery.

1. Protocol (see phase 2)

#### RESEARCH STRATEGY

#### **SIGNIFICANCE**

Disruptive behavior disorders are a substantial and under-treated public health threat. Disruptive behavior disorders in young children are highly prevalent, with ODD and ADHD each affecting over 10% of preschool-aged children (Lavigne et al., 2009). Such disorders often persist into adolescence (Thompson et al., 2011), raising the likelihood of negative outcomes such as substance use (Moffit, Caspi, Dickson, Silva, & Stanton, 1996). Further, as children grow, disruptive behavior problems become more severe and treatment resistant (Ruma, Burke, & Thompson, 1996). A number of parent training (PT) programs have shown clear efficacy in preventing (Dishion et al., 2008) and treating (Eyberg et al., 2001; Reid, Webster-Stratton & Hammond, 2003; Sanders, Markie-Dadds, Tully, & Bor, 2000) disruptive behavior disorders in young children. These programs have common elements, such as teaching strategies to prevent and respond to children's disruptive behavior. Unfortunately, only 3% of young children with emotional or behavioral disorders receive any treatment at all (Lavigne et al., 2009), and rates of receiving evidence-based PT are likely lower. Further, of families who do sign up for PT, 40% never complete a treatment session (Fernandez, Butler, & Eyberg, 2011); of those who complete at least one session, approximately half drop out early (Beveridge et al., 2015). Disruptive behavior disorders in young children are prevalent, consequential, and under-treated. Strategies taught in PT are effective, but are reaching only a minority of parents in need.

Parents face many barriers in connecting with evidence-based parenting training. As reviewed by [name] and [name] (2015a), many barriers prevent families from receiving traditional services for children's disruptive behaviors. For example, there is a well-recognized shortage of mental health services for children (Cummings, Wen, & Druss, 2013); waitlists are common (Sherman, Barnum, Buhman-Wiggs, & Nyber, 2009; Werba et al., 2006); and many parents do not know where to find help (Pavulri, Luk, & McGee, 1996). Further, many families faced with significant disruptive behavior do not even recognize there is a problem in need of attention (Girio-Herrera, Owens, & Langberg, 2012; Pavulri et al., 1996). Other parents adopt a "wait and see" approach and defer seeking help (Girio-Herrera et al., 2012). Creative solutions are needed to overcome barriers and to connect parents with PT interventions.

**Technology may be an ideal response.** A technology-based response can (a) be implemented in healthcare settings, thus increasing access and identification of at-risk children; (b) provide motivational content designed to promote use of PT; and (c) provide more tailored online treatment with minimal barriers. The vast majority of children in the U.S. receive regular health care from a doctor's office (Bloom, Jones, & Freeman, 2012), and current guidelines encourage incorporating mental health screening, parenting information, and mental health treatment into pediatric healthcare visits (Hagan, Shaw & Duncan, 2008). Notably, self-administered PT in healthcare settings (i.e., giving parents packets outlining evidence-based parenting skills) shows promise for responding to confirmed disruptive behavior diagnoses as well as elevated levels of disruptive behavior problems in young children (Berkovtis et al., 2010; Lavigne et al., 2008). Technology could greatly enhance this self-administered approach to responding to disruptive behavior problems. Importantly, as access to the Internet becomes ubiquitous—even among low-income populations (Zickuhr & Smith, 2013)—internet-based PT becomes an increasingly viable solution to dissemination-related barriers. Using an NIH-recommended intervention development framework, the **ORBIT model** (Czajkowski et al., 2015), this project will develop a technology-based parenting system, the "Parenting Young Children Check-Up" (PYCC), which will dramatically increase the reach of PT through motivating use of an evidence-based PT website.

#### INNOVATION

The PYCC will include two elements: 1) an initial check-up (level 1; delivered in healthcare settings) designed to increase identification of potentially problematic levels of disruptive behavior and an interactive **brief motivational intervention** (<20 minutes), with subsequent tailored email and text messages; and 2) an associated PT website that teaches specific parenting skills. Email and text messages will guide parents through the website.

Several key, innovative features will be incorporated into the PYCC to help it to overcome barriers limiting other PT approaches, including:

 A proactive approach. Traditional PT models wait for parents to seek help from professionals before services are delivered. The PYCC proactively identifies at-risk families using universal screening in a healthcare setting, and subsequently uses motivational techniques to facilitate use of the online tool.

- 2. Tailored Internet-based PT. Available online programs progress through preset modules (e.g., Sanders et al., 2012; Sourander et al., 2016) rather than responding to parent input. The PYCC will capitalize on computerized program capabilities and tailor the progression of content based on parent input.
- 3. Lifelike, synchronous interactivity with empathic reflections. The literature on human-computer interactions indicates that people interact with computers as if they are humans, especially when the computer has lifelike characteristics (Nass & Moon, 2000). Additionally, people respond positively to computer programs that express positive regard and empathy (Bickmore, Caruso, Clough-Gorr, & Heeren, 2005). Both levels of the PYCC will have a positive, empathic animated narrator that does the "talking" through the program in order to engage parents and facilitate learning.

#### **APPROACH**

## **Preliminary data**

Is there a need for non-traditional PT? An examination by the PI of PT in a statewide rollout (see Candidate's Background) showed that nearly 60% of families receiving PCIT dropped out early (Beveridge et al., 2015). Notably, this investigation only considered treatment seeking parents; attrition among non-treatment seekers would likely be higher. Recently, the PI and her mentor found that the majority (70%) of parents who rated their young children in the "at risk" range for behavioral health problems had not sought help and did not think it necessary. Relying on parent help-seeking leads to under-identification.

Do parents support a technology-based approach in health care? The PI's data, collected from a group of 50 diverse and low-income parents at Detroit childcare centers, suggests that many parents are already using technology to get information about children's challenging behavior and parenting, and are open to expanding the ways in which they do so. Of the parents surveyed, 100% reported access to the Internet, 74% said they use the Internet to get information about parenting and/or child behavior, and 20% regularly use the Internet to get information about parenting and/or child behavior ([name] & [name], 2015b). Further, parents reported high levels of openness to using tablets at healthcare visits to do behavioral screening (78% agreed) and to receive information about parenting (84% agreed; [name] & [name], 2015b).

Do health care physicians support a technology-based approach? The PI and her primary mentor have also examined physicians' reported need for, and openness to, a technology-based approach to promoting behavioral health for young children (see [name] & [name], 2015b). Sixty pediatricians were recruited at Children's Hospital of Michigan (CHM) and completed brief surveys. Over 70% agreed they would like patients to complete pre-visit behavioral health screening on tablets. Nearly 90% reported openness to parents getting information about parenting and child behavior on tablets in the waiting room; and over 90% agreed they were open to recommending a parenting website.

## Theoretical models

[figure not shown]
Two theoretical models will guide intervention development and evaluation. First, the technology acceptance model (TAM; Davis, 1989) suggests use of new technology is highest when users perceive it as easy to use (i.e., requiring low effort) and useful (i.e., use will positively impact the users' performance). Design of the system will center on creating a system that is perceived as easy to use and useful. Second, the Theory of Planned Behavior

(TPB; Ajzen, 1991) suggests that key beliefs, including attitudes, subjective norms, and perceived control, motivate behavior through their effect on change intentions. As depicted in Figure 1, mechanisms linking completion of the initial check-up (level 1) with use of the PT website (level 2) may be consistent with the TPB. That is, the initial check-up (level 1) will motivate use of the PT website (level 2) by altering parents' attitudes towards children's behavior, perceptions of child behavior norms, and perceived control over child behavior.

#### **Proposed intervention**

Although page limits prohibit an exhaustive description of the intervention, Figure 2 provides an overview of key proposed PYCC processes and content. As previously mentioned, there will be two main parts to the intervention: An initial check-up completed on a tablet at a healthcare visit (level 1), and a PT website that aims to teach specific skills that are common elements of behavioral PT programs (level 2; reviewed interventions

include Parent-Child Interaction Therapy [Zisser & Eyberg, 2010], The Incredible Years [Webster-Stratton et al., 2013], Brief Behavioral Intervention [Axelrad, Butler, Dempsey, & Chapman, 2013], Parent Management Training [Patterson, Reid, & Dishion, 1992], and Triple P [Sanders, Bor, & Morawska, 2007]). Both levels will incorporate an animated narrator and high quality, professionally made videos featuring professional actors (further information below). While parents will be encouraged to access all content on the PT website, parents will have input regarding how they move through the content and, ultimately, what content they use (creating a tailored intervention); this is similar to the tailoring done in the evidence-based Family Check-up (Gill, Hyde, Shaw, Dishion, & Wilson, 2008) as families choose the number and focus of intervention sessions. This choice will be made by parents as part of the initial check-up (see Figure 2b). The two intervention levels will be connected through text and email messaging (see Figure 2c for an example), which will prompt parents to complete sessions. Importantly, intervention creation will be highly influenced by all aspects of the training plan—allowing the candidate to transform gained knowledge into hands-on experiences creating a motivational mHealth intervention (training goal 1), carrying out qualitative data collection (training goal 2), and incorporating the PYCC into the work flow of a health care visit (training goal 3). Further, following the ORBIT framework, specific content will be influenced by data collected during the "Define & Refine" stage (see Figure 3. Step 2). Input from parents and professionals will guide specific decisions about presentation of materials. frequency of contact (e.g., frequency of messages), and presentation of content, in order to maximize technology acceptance.

1tailored based on screening results (e.g., severity of DBP; current motivation to change); 2tailored based on goals

Technical aspects of program creation. The initial check-up will be programmed using the Computerized Intervention Authoring System (CIAS), a web-based authoring tool that allows the creation of highly interactive brief interventions without the need for programming. Consistent with the Elaboration Likelihood Model (Petty & Cacioppo, 1986), which posits that tailoring health content to the individual increases perceived relevance, system logic within CIAS enables branching and tailoring. That is, content is presented in a customized manner, dependent on prior responses. Interventions created through CIAS have been successfully used by parents in multiple previous randomized trials, and these parents have given high ratings for ease of use (e.g., [name] et al., 2014). The most recent version of CIAS deploys as a cross-platform compatible mobile web app, making it accessible on any mobile device, and is also able to send tailored emails and text messages.

The level 2 PT website will be created using Wix.com. Wix is a user-friendly platform allowing individuals without programming experience to create sophisticated HTML5 websites that use responsive web design, making them compatible with mobile devices of all types and sizes. The website will be created by the PI and project RA. Given how important ease of use is, a Wix programming consultant will be hired in year 1 in order to generate suggestions for improvements. The website will be username protected. Wix websites are highly flexible and scalable, and also allow for implementation of custom coding if necessary.

#### Research Design

**Introduction and overview.** As seen in Figure 3, the research project—and complimentary training activities—will follow the steps outlined in the NIH ORBIT framework (Czajkowski et al., 2015). In step 1 (complete), the PI and her primary mentor identified the limited reach of traditional PT programs and proposed an approach to expand the reaching using technology (see [name] & [name], 2015a). The proposed K

award period will focus on the early stages of intervention development and evaluation. The culmination of the project will be preparation of an NIMH R01 application to conduct a fully powered RCT.

Figure 3. Overall project de	esign and timeline			
Steps using ORBIT framework	rk (Czajkowski et al., 2015)			
Identify a clinically significant question	2. Define and Refine	3. "Proof of Concept" trial	4. Initial RCT	5. Efficacy Trial
Specific steps to develop the	PYCC			
a) Review of barriers to     PT and innovative     approaches     b) Identification of     common PT elements	a) Qualitative interviews with 12-20 parents b) Qualitative interviews with 12-20 professionals c) Creating, editing, and refining based on input	a) 20 parents complete initial check-up (level 1) b) Parents will rate ease of use, usefulness, and intention to use the parent training website (level 2)	a) Parents recruited in waiting rooms randomized to complete initial check-up or control condition b) 1 and 3 month follow-ups c) R01 submission	a) Fully powered RCT b) Use mixed methods including parent-report, observations, and qualitative interviews
Timeline				
Complete; see [name] & [name], 2015	K01 Award Period Phase 1 (Yrs. 1 & 2)	K01 Award Period Phase 2 Year 3	K01 Award Period Phase 3 Year 4	R01 (Anticipated)

For each phase, parent-participants will be parents of young children (ages 2-5; an age when parents are central change agents for children's behavior) who report elevated child disruptive behavior problems. Parents will complete the The Eyberg Child Behavior Inventory (ECBI; Eyberg & Pincus, 1999); a widely used measure in PT research (e.g., see Reyno & McGrath, 2006). Those with a t-score at/above 55 ("at risk" range and above; capturing clinical and sub-clinical levels) will be invited to participate further. We anticipate 20% of screened children will be eligible. All screened parents will receive a \$5 gift card.

## Phase 1: Define and Refine (Yrs. 1 & 2)

**Overview.** The first two years of the K01 award period will focus on creating an mHealth intervention that aligns with parent and professional input. Specifically, consistent with the ORBIT model, we will finalize the process and content for both intervention levels, using **qualitative input** from parents and professionals.

Input from physicians: We look to develop a process of delivering the initial check-up (level 1) in healthcare settings in a way that minimizes burden to professionals. As such, a central part of developing and refining the system is seeking feedback from physicians (consistent with the ORBIT model; see Czajkowski et al., 2015). We will seek qualitative data from physicians examining behavioral health care, and openness to the proposed PYCC system. Data collection will continue until saturation is reached (anticipating12-20 participants). To accommodate the schedule of physicians, these will be conducted as one-on-one interviews. A detailed qualitative agenda will be prepared through collaboration with the qualitative mentor and consultant. Participating professionals will receive a \$30 gift card.

Input from healthcare professionals: A necessary component of the success of the PYCC is that it fits in with office flow at busy pediatric practices. To ensure this, we will have a focus group with 5-10 pediatric office staff (i.e., medical assistants, receptionists). The focus group will be no more than 40 minutes in length and will take place during a regularly scheduled lunch meeting. Lunch will be provided for staff that participate. A qualitative agenda will guide the focus group; staff will learn about the PYCC and give feedback and suggestions. Participants will receive a \$30 gift card.

**Input from parent-participants.** It is critically important that the PYCC is engaging and perceived as useful to parents. A convenience sample of parents of children ages 2-5 will be recruited through email and face-to-face solicitation at drop-off and pick-up times at the centers. Just as with all parent participants, the ECBI will determine eligibility. Parents will complete one-on-one qualitative interviews. The PI will create a qualitative agenda to guide the interviews and will personally conduct half of the interviews.

**Initial content development and presentation**. Phase 1 participants will learn about planned intervention process and content—seeing examples of questions, text/email messages, and example videos. In terms of videos, video content will initially be made in GoAnimate (www.goanimate.com) in order to make cost-effective examples of content. Following parent input, high quality videos will be produced through a partnership with Wayne State's University Television, which consists of a team of video production professionals who will

partner with the PI and mentorship teams members on video conceptualization, pre-production, and editing. The goal will be to have a full beta version of the intervention, including high quality videos, that was developed with extensive input from professionals and parent by the end of the second year.

Feedback data extraction. All qualitative interviews and focus groups will be audio recorded and transcribed. As part of the training in qualitative research (Training Objective 2), the PI will learn two types of qualitative. In order to meaningfully examine professional and parent qualitative data, framework matrix analysis will be used for this project to extract, summarize, and analyze interview data (thematic analysis will also be complete with collected data as a training experience). In this efficient qualitative data analysis approach, summaries are assigned thematic categories derived a priori rather than de novo based upon the interview agenda. This process will yield specific, recurring information about participant feedback. Results will be discussed with mentors and will inform changes.

## Phase 2: Proof of concept testing (Yr. 3)

**Overview.** "Proof of Concept" testing, as outlined by the ORBIT model (Czajkowski et al., 2015), will be completed using a non-randomized design. This phase will allow us to determine acceptance and impact of the PYCC initial check-up on intention to use PT website. It will also allow us to get further input from parents before the RCT data collection year; time will allow for final modifications to the program content (e.g., videos) and process if needed. Finally, participants will be recruited from the same locations as will be used for the RCT, allowing for refining of data collection procedures prior to the RCT.

Participants and Procedures. Parents will be recruited from the Henry Ford Health Systems Pediatric clinic at New Center One in Detroit, Michigan. Recruitment approach will follow procedures used in multiple NIH-funded investigations (PI: [name]). This recruit approach does create downtime for the RA, but it is necessary in order to be in line with HIPAA regulations and incorporate data collection into health care office flow. The RA will be able to make use of down time by working to manage deidentified data (among other tasks). The project RA will work with office staff to know what times potential participants will be seen. The study will be introduced to parents by front office staff, Medical Assistants, or physicians for well-child visits for children 2-5. If the parent expresses interest in participating, the project research assistant will meet with him/her (either before or after the visit, depending on time) and provide further detail about participation. All parents of children ages 2-5 that agree to participate (*n* = 75) will complete the brief screener (i.e., the ECBI; Eyberg & Pincus, 1999) to determine further eligibility. If eligible, the parent will use a study tablet to answer questions, go through phase 1 of the PYCC, and provide brief feedback. Parents will also receive a list of URLs to access parenting videos and (if they choose) can view the videos and provide feedback (this element is not required for participation). We intent for participation to take <20 minutes; research staff will be mindful not to disruptive office flow. Participants will be compensated with a \$25 gift card for their time.

Measures and Procedures. Parents will do the full initial check-up (level 1) at the health care visit, then complete a brief questionnaire intended to evaluate perceptions of 1) ease of use, 2) usefulness of the information (in line with the Technology Acceptance Model; Davis, 1989), and 3) intentions to use the PT website (level 2). Items will be rated on a 1 (strongly disagree) to 5 (strongly agree) scale. Parents will also answer some brief, open-ended questions in order to tap into perceptions of the system and any barriers to using the PT website (level 2). After 5 parents participate, ratings will be examined. Literature on technology development suggests 5 users is generally sufficient for early testing (Turner, Lewis, & Nielsen, 2006). We seek to obtain quantitative ratings exceeding 4 on a 1-5 scale, and positive qualitative feedback. If this goal is not reached, we will recruit an additional 5 parents, in blocks, as needed (we anticipate needing 5-15 parents).

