#### Phase 3: Pilot RCT (Yr. 4)

**Overview.** Forty parents of young children will be randomized to intervention (i.e., initial check-up [level 1]) or control conditions (i.e., assessment only), with follow-up assessments at 1-month and 3-months.

**Participants and Procedures.** Parent recruitment methods will be identical to those described in Phase 2. A second assistant (i.e., a research technician) will be hired at the beginning of this year in order to make recruitment feasible. Participating parents will be compensated \$25 for baseline participation, \$25 for completing the 1-month follow-up, and \$50 for completing the one-month follow-up.

**Randomization.** Randomization will be automatically generated by CIAS. Parents randomized to the control condition will only complete the evaluation measures (see Table 1) and select goals. Parents randomized to the intervention condition will complete the full initial check-up (Level 1; see Figure 3b). All parents (both

control and intervention) will be given a brochure to access the PT website by the research assistant; including unique login number that will allow us to examine if completing the full initial check-up impacts website use.

**Follow-up.** We will follow up with participants in both conditions by sending links to online surveys at one month and three months after baseline (these questionnaires will be done through Qualitrics; see www.qualtrics.com). Parents will complete all evaluation measures (Table 1) at each time point. We will communicate by phone and by regular email with participants who do not complete the survey in an attempt to prompt participation or establish that the participant is choosing to stop their participation.

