Measures. Table 1 outlines measures used for evaluation, the construct each measure taps into, and assessment points for each measure. The primary outcome of interestuse of the PT website-will be measured via rates of visiting the website for each assigned user ID (gathered via using Google Analytics). The secondary outcome of focus, items consistent with the TPB, will be measured with items made specifically for this project; rated on a 5-point scale with 3 items tapping into each domain. Internal consistency will be examined for the measure as a whole and item domains. As mentioned previously, the ECBI will be used to screen children for disruptive behavior problems. The ECBI taps into parents' perceptions of child disruptive behavior through 36-items in which caregivers rate the frequency of specific challenging child

Table 1: Evaluation N	Measures			
Construct	Measure name (author)		Assessment P	oint
	· ,	BL	1-month	3-month
Disruptive behavior problems	Eyberg Child Behavior Inventory (ECBI; Eyberg & Pincus, 1999; Intensity and Problem scales)	х	х	х
Parenting practices	Alabama Parenting Questionnaire—Preschool Revision (Clerkin, Marks, Policaro, & Halperin, 2007)	x	Х	x
		X	X	X
Parents' Theory of Planned Behavior (TPB)	Items made specifically for this project with three items tapping into each domain of TPB			
Use of Parenting Training Website	Tracking of username logins through Google analytics tool		х	X
Technology Acceptance Questionnaire (intervention group)	Items made for this project tapping into ease of use, usefulness, and overall satisfaction	х	х	х

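### Should Phase 2 have rehearsed the login tracking that supplies the pilot RCT's primary outcome?

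*Combined protocol and SAP*

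**What the plan says.** **Phase 2 (Participants and Procedures; Measures and Procedures).** Parents complete the check-up on a tablet, then rate ease of use, usefulness and "3) intentions to use the PT website (level 2"), each on a 1-5 scale, and answer open-ended questions. For online content the plan says: "Parents will also receive a list of URLs to access parenting videos and (if they choose) can view the videos and provide feedback". Viewing is optional. The Overview adds that recruiting at the sites to be used for the RCT has a benefit, "allowing for refining of data collection procedures prior to the RCT".

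**Phase 3 (Randomization; Measures; Table 1).** Both arms receive a brochure for the website, "including unique login number that will allow us to examine if completing the full initial check-up impacts website use". The primary outcome is measured by "rates of visiting the website for each assigned user ID (gathered via using Google Analytics"), and Table 1 schedules it at 1 and 3 months.

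**Elsewhere.** Under Proposed intervention, the technical description says of the site: "The website will be username protected". It does not say that Phase 2 parents are given usernames. The cover letter describes Phase 2 website interest as self-report only: "parents reported if going through the first parent of the program led them to want to use the program parent training website".

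**The concern.** The programme's premise is that the check-up in the clinic moves parents on to the website. Phase 2 is the last step before the RCT, and its Overview mentions refining data collection. Recruitment, screening and tablet delivery all get a trial run. The chain from issued login to recorded visit to correct ID gets none that the plan describes.

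What is at stake is a silent error. If visits under an ID are not recorded, the parent appears in the data with zero visits. That is not a missing value, so the multiple imputation planned for participants lost to follow-up would leave it untouched. With 20 parents per arm there is little room to absorb such losses, and the plan already concedes low power.

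**Working it through.** **1. What each phase exercises**

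| Element | Phase 2 | Phase 3 |
|---|---|---|
| Clinic recruitment, ECBI screen, tablet check-up | yes | yes |
| Ease of use and usefulness ratings | yes | yes (intervention arm) |
| Intention to use the website | yes, 1-5 rating | within the Theory of Planned Behavior items |
| Randomization through CIAS | no (non-randomized) | yes |
| 1- and 3-month online surveys | none described | yes |
| Unique login, visits per user ID | none described | yes |

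The factual premise is right: no login tracking is described for Phase 2. But tracking is one of several Phase 3 components not tried there. The sentence on refining procedures is tied to the choice of recruitment sites. The aim given at the start of the same Overview is acceptance, and the effect of the check-up on intention. The passages do not contradict each other.

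**2. Inputs**

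The plan states no figure for tracking failure, so there is none to reproduce. The sizes are:
- Phase 2: 5-15 parents anticipated. The screening numbers agree with the top of that range: 75 × 20% = 15. The cover letter reports 6 enrolled.
- Phase 3: 20 per arm.
- Fault rate f, the share of IDs whose visits are not recorded: not in the documents; 10%, 20% and 30% are assumed.

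**3. What a fault would do in Phase 3**

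One ID is 1/20 = 5% of an arm. If faults are equally common in both arms and unrelated to use, the expected raw difference in mean visits is (1 − f) × the true difference, so f = 20% removes 20% of it.

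The planned effect size is Cohen's d, whose SD changes too. With mean m and SD s taken as similar in the two arms, the recorded variance is (1 − f)s² + f(1 − f)m², so d is multiplied by √[(1 − f)/(1 + f·m²/s²)]. At f = 20%:
- s much larger than m: √0.8 = 0.894, a loss of about 11%.
- s equal to m: √(0.8/1.2) = 0.816, a loss of about 18%.

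**4. What a Phase 2 check could have shown**

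If each login is tried once and faults are independent, P(at least one failure) = 1 − (1 − f)^n:

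| f (assumed) | n = 5 | n = 6 | n = 15 |
|---|---|---|---|
| 10% | 41% | 47% | 79% |
| 20% | 67% | 74% | 96% |
| 30% | 83% | 88% | 99.5% |

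A clean result in 6 parents would leave a one-sided 95% upper bound of 1 − 0.05^(1/6) = 39% on the fault rate.

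**5. Which faults need parents to find them**

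The table assumes sporadic, independent failures. A wrongly configured analytics tool would probably affect every ID, and one test ID would then show it. Only sporadic faults call for real users, and those are the ones that 5-15 parents detect unreliably unless they are common.

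**6. Effect on Phase 2**

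The Phase 2 results are the ratings, with a target above 4, and the open-ended feedback. None depends on a login or a visit count.

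**The case for a change.** The best case for a change is that it would have been cheap. The login and analytics tool were already planned, and a full beta version was due by the end of year 2. Phase 2 parents could have been handed the Phase 3 brochure in place of video links. A real parent at home, on their own phone, exercises the chain in a way that staff cannot. A blocked login is not always reported either: a parent may simply give up, and the zero looks the same. A small observed use count beside the intention rating would also have been informative, since intention is not use.

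Part of this stands. It was an opportunity not taken, and silent zeros are a real way for this outcome to go wrong. But nothing in the documents points to a tracking fault, and the fault rates above are invented for illustration. A use count from 6 parents without a control group would not serve as a planning rate: 0 of 6 leaves a two-sided 95% upper limit of 1 − 0.025^(1/6) = 46%. Tracking would also add a follow-up window and its disclosure to a single visit meant to last under 20 minutes, and a supervised trial login could itself affect later use. The documents do not pass intention off as use; the cover letter and Phase 2 both speak of wanting or intending to use the website.

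**Conclusion.** The observation is accurate, but it does not call for a change. Phase 2 was set up to learn whether parents accept the check-up and intend to go on to the website, and its measures match that aim. The tracking mechanism is first used in a 40-parent pilot RCT that precedes a fully powered trial, and finding out whether a measurement works is a normal job for such a pilot. Confirming with test IDs that logins open the site and that visits reach the right ID is ordinary set-up work, which a competent team does before launch whether or not a grant-style research strategy says so.

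On size: for Phase 2 the effect is nil. For Phase 3, each unrecorded ID would cost 5% of an arm, and an assumed 20% fault rate would take 20% off the raw difference and about 11% to 18% off Cohen's d, the last range holding when the SD of visits is at least as large as the mean. These figures assume faults that are equal across arms and unrelated to use. Phase 2 collection is reported as complete, so login tracking can no longer be added to it. The conclusion rests on the text available; a few parts of the document could not be checked.
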